positive human immunodeficiency virus (HIV) antibody, or active syphilis (positive treponema pallidum particle agglutination assay [TPPA] with positive rapid plasma reagin [RPR] test);

- History of allergic reactions to hUC-MSC-sEVs, hyaluronidase, or excipients in the study drug;
- Known atopic diathesis (e.g., severe asthma, urticaria requiring systemic treatment);
- Nasal structural abnormalities or lesions that affect drug delivery (e.g., severe nasal septal deviation, nasal polyps, chronic sinusitis with acute exacerbation);
- Cerebrospinal fluid rhinorrhea (spontaneous or post-traumatic);
- Participation in other interventional clinical trials within 3 months prior to screening;
- Unwillingness or inability to comply with protocol-specified procedures (e.g., refusal to undergo required imaging examinations);
- Pregnant or lactating women (confirmed by urine pregnancy test for women of childbearing potential); women of childbearing potential who cannot or refuse to use effective contraceptive measures (e.g., combined oral contraceptives, intrauterine device) during the study and for 3 months after the last dose;
- Uncontrolled psychiatric disorders (e.g., schizophrenia, major depressive disorder with suicidal ideation) that affect compliance;
- Other conditions deemed unsuitable for enrollment by the investigator (e.g., terminal illness with life expectancy <6 months).

(3) Records of Failed Screening

- Investigators are responsible for all subjects who have signed the informed consent form, regardless of whether they are ultimately enrolled.
- If a subject is deemed ineligible during screening (at the first visit), the investigator shall complete the "Screening Failure Form" (attached to the CRF) and document the specific reason for failure (e.g., "NIHSS score = 4 < 6", "History of mechanical thrombectomy"). The screening number assigned to the ineligible subject shall not be reused.

(4) Criteria for Determining Lost-to-Follow-Up Subjects

A subject is considered lost to follow-up if:

- They experience an AE, SAE, or other complication that requires study termination and urgent treatment, as judged by the investigator;

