- Their condition of a concurrent disease (excluding the index stroke) deteriorates, requiring alternative treatment that conflicts with the study protocol; if the subject's stroke condition deteriorates after receiving hUC-MSC-sEV-001 (e.g., progression of neurological deficit), they shall withdraw from the study and be classified as an invalid case (not a lost-to-follow-up case);
- They have poor compliance (e.g., missed ≥ 2 scheduled visits, refusal to undergo required assessments) or express unwillingness to continue the study;
- They are lost to contact for ≥ 2 weeks despite repeated attempts (e.g., telephone, text message, home visit).

For lost-to-follow-up subjects, the investigator shall make every effort to complete the final safety assessment (e.g., vital signs, adverse event recording) and document the reason for withdrawal in the CRF.

(5) Provisions for Excluded Cases

A case is excluded from the efficacy analysis set if:

- The subject is misdiagnosed (e.g., final diagnosis is transient ischemic attack rather than ischemic stroke);
- The subject meets the inclusion criteria but is not administered any dose of hUC-MSC-sEV-001, or fails to receive scheduled doses due to production failure of the study drug;
- The subject participates in another interventional clinical trial during the study period;
- The subject receives prohibited combined medications (e.g., antineoplastic drugs, neurotrophic factors) or non-protocol-specified treatments that affect efficacy assessment;
- The subject has no evaluable efficacy data (e.g., no post-baseline NIHSS or mRS assessment);
- The subject has severe protocol violations (e.g., administration of the wrong dose, missed ≥ 3 doses).

Excluded cases shall be documented in the "Protocol Deviation Log", and their CRFs shall be retained for audit. Subjects who receive at least one dose of the study drug and have safety data shall be included in the safety analysis set.

(6) Criteria for Terminating or Withdrawing from the Study

i. Study Termination

Study termination refers to the early cessation of the entire study before completion of the planned protocol. The decision to terminate the study shall be made by the sponsor, principal investigator, or Ethics Committee, and shall be documented in the "Study Termination Report". Reasons for termination include:

- Emergence of SAEs that suggest a causal relationship with the study drug and pose a serious risk to subjects;

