- Confirmation of the MTD or identification of an unsafe dose level;
- Major flaws in the study design that affect data validity;
- Regulatory requirements (e.g., request by the National Medical Products Administration [NMPA]).

. Subject Withdrawal

Subjects may withdraw from the study at any time for the following reasons:

(1) Investigator-determined withdrawal:

① The subject develops a medical condition that makes continued participation unsafe (e.g., severe allergic reaction, intracranial hemorrhage);② The subject uses medications that interact with the study drug (e.g., immunosuppressants) or affect efficacy assessment (e.g., edaravone);③ The subject experiences a SAE that requires termination of study participation;④ The subject has poor compliance that compromises the reliability of safety or efficacy data.

(2) Subject-initiated withdrawal:

① The subject voluntarily requests to withdraw (no reason required);② The subject is lost to follow-up (no contact for ≥ 2 weeks).

For withdrawn subjects, the investigator shall conduct a final safety assessment (if possible) and document the reason for withdrawal in the CRF. Subjects who withdraw due to AEs/SAEs shall receive appropriate medical treatment, and follow-up shall continue until the AE/SAE resolves or stabilizes.

(7) Criteria for Terminating the Study

The study will be terminated immediately if any of the following occurs:

≥ 2 subjects experience DLT at the same dose level (indicating that the dose exceeds the MTD);

- Production of hUC-MSC-sEV-001 fails to meet quality standards for 3 consecutive batches, resulting in inability to administer scheduled doses;

- The study drug is found to have no clinical benefit (e.g., no improvement in neurological function in all enrolled subjects) or is associated with unexpected severe toxicity;
- A major protocol deviation is identified (e.g., incorrect randomization, unapproved dose modification) that invalidates the study results;
- The sponsor terminates the study due to funding, strategic adjustments, or other reasons;
- The Ethics Committee or NMPA issues an order to terminate the study.

3. Intervention Measures

(1) Trial Drug

- **Generic Name:** Human Umbilical Cord Mesenchymal Stromal Cell-Derived Small Extracellular Vesicle (hUC-MSC-sEV-001) Nasal Drops
- **Source:** Isolated and purified from the supernatant of hUC-MSCs cultured under GMP conditions

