1. **Dose Adjustment:** No dose reduction is allowed during the study. If a subject experiences a Grade ≥ 3 AE, study drug administration is suspended until the AE resolves to Grade ≤ 1 ; if the AE is judged to be related to the study drug, the subject withdraws from the study.

2. **Prohibited and Restricted Medications:**

- Prohibited medications: Antineoplastic drugs, immunosuppressants (e.g., cyclosporine, tacrolimus), neurotrophic factors (e.g., nerve growth factor);
- Restricted medications: Antibiotics and antiviral drugs (used only for confirmed infections, with duration documented); non-steroidal anti-inflammatory drugs (NSAIDs) (avoided if possible to reduce bleeding risk).

3. **Concurrent Diseases Management:** If a subject develops a concurrent disease (e.g., pneumonia, myocardial ischemia) during the study, the treating physician provides standard treatment, and the details are documented in the "Concurrent Disease Record Form" in the CRF.
4. **Subject Education:** Subjects are instructed to report any new symptoms (e.g., headache, nasal congestion, rash) to the investigator immediately, and to avoid self-medication with prohibited drugs.

4. Observation Items

(1) Demographic and Clinical Data

1. **Demographic Characteristics:** Gender, age, date of birth, ethnicity, dominant hand, occupation, height, weight, body mass index (BMI);
2. **Clinical History:** Chief complaint, onset time of stroke, detailed history of present illness, primary diagnosis (including infarct location), secondary diagnoses, past medical history (hypertension, diabetes, hyperlipidemia, coronary heart disease), surgical history, allergy history, family history, smoking history (pack-years), drinking history (alcohol consumption per week);
3. **Medication History:** Current medications (including over-the-counter drugs, herbal supplements) at screening, with dosage, frequency, and duration documented.

All data are recorded in the "Baseline Demographic and Clinical Data Form" in the CRF.

(2) Safety Observation Indicators

1. **Vital Signs:** Measured before each dose administration and at each follow-up visit:
 - Pulse (beats per minute), blood pressure (mmHg, measured in the sitting position after 5 minutes of rest), respiratory rate (breaths per minute), body temperature (°C, axillary or oral);
 - Abnormal vital signs (e.g., hypertension: systolic blood pressure ≥ 160 mmHg) are documented and followed up.
2. **Laboratory Tests:**

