1. Neurological Function Scales:

- **NIHSS:** Assesses the severity of neurological deficits (range: 0-42; higher scores indicate more severe deficits). Administered at baseline, Day 7, Day 14, and Day 90.
- **mRS:** Assesses functional independence (range: 0-6; scores 0-2 indicate good functional outcome). Administered at baseline, Day 7, Day 14, and Day 90.
- **Modified Barthel Index (MBI):** Assesses activities of daily living (range: 0-100; higher scores indicate better independence). Administered at baseline, Day 14, and Day 90.
- **EQ-5D-5L:** Assesses health-related quality of life (including mobility, self-care, usual activities, pain/discomfort, anxiety/depression; scored as a utility value ranging from -0.291 to 1.0). Administered at baseline, Day 14, and Day 90.

2. Cerebral Perfusion Parameters (CTP):

- Measured at baseline, Day 14, and Day 90: cerebral blood volume (CBV), cerebral blood flow (CBF), mean transit time (MTT), time to peak (TTP) in the infarct core and penumbra.
- Changes in perfusion parameters from baseline are used to evaluate the improvement of cerebral blood flow.

3. Infarct Volume Measurement:

- Infarct volume is measured on DWI using the ABC/2 method (A: maximum length, B: maximum width perpendicular to A, C: number of slices × slice thickness).
- Changes in infarct volume from baseline to Day 14 are used to evaluate infarct progression or regression.

5. Outcome Evaluation Indicators

(1) Primary Safety Endpoints

- **Dose-Limiting Toxicity (DLT):** Assessed within 14 days of the first dose, defined as any of the following:
 1. Grade 3-4 AE related to the study drug (CTCAE V5.0), such as severe nasal bleeding, anaphylactic reaction, or hepatic injury;
 2. Increase in NIHSS score ≥ 4 points from baseline (indicating significant neurological deterioration);
 3. Symptomatic intracranial hemorrhage (confirmed by CT/MRI and associated with neurological deterioration).

(2) Secondary Safety Endpoints

1. **SAE Incidence:** Proportion of subjects with drug-related SAEs within 90 days of the first dose;
2. **All-Cause Mortality:** Proportion of subjects who die from any cause within 90 days of the first dose;
3. **Laboratory Abnormality Rate:** Proportion of subjects with Grade ≥ 3 laboratory abnormalities (e.g., thrombocytopenia, elevated liver enzymes) within 90 days.

(3) Efficacy Endpoints

1. **Functional Outcome:** Proportion of subjects with mRS score 0-2 at Day 90;

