- **Grade 1-2 AEs:** Monitor closely; provide symptomatic treatment if needed (e.g., antihistamines for mild rash). Continue study drug administration if the AE is judged to be unrelated or unlikely related to the study drug.
- **Grade 3-4 AEs:** Suspend study drug administration immediately; provide urgent medical treatment (e.g., corticosteroids for severe allergic reactions). The investigator assesses the causal relationship between the AE and the study drug. If the AE is related or probably related, the subject withdraws from the study, and follow-up continues until the AE resolves or stabilizes.
- **SAEs:** Implement the following emergency procedures:
 1. Provide immediate medical treatment to stabilize the subject's condition;
 2. Notify the principal investigator, sponsor, and Ethics Committee within 24 hours of awareness;
 3. Complete the "Serious Adverse Event Report Form" and submit it to the Ethics Committee and sponsor;
 4. Conduct follow-up assessments until the SAE resolves or stabilizes, and submit follow-up reports every 7 days until resolution.

(4) Assessment of Causal Relationship Between Adverse Events and Study Drug

The causal relationship is assessed by the investigator based on the following five factors:

1. **Temporal Relationship:** Whether the AE occurred after administration of the study drug (onset time within the drug exposure period);
2. **Known Pharmacological Effects:** Whether the AE is consistent with the known safety profile of MSC-sEVs (e.g., nasal irritation is a potential local effect);
3. **Decchallenge Response:** Whether the AE resolved or improved after discontinuing the study drug;
4. **Rechallenge Response:** Whether the AE recurred after re-administering the study drug (not applicable in this study due to safety concerns);

5. **Alternative Etiologies:** Whether the AE can be explained by the subject's underlying disease, concurrent medications, or other factors.

The causal relationship is classified into five categories:

- **Definite:** All five factors support a causal relationship;
- **Probable:** Four factors support a causal relationship, and no alternative etiology is identified;
- **Possible:** Three factors support a causal relationship, and alternative etiologies are possible;
- **Unlikely:** Two or fewer factors support a causal relationship, and alternative etiologies are likely;
- **Unrelated:** No factors support a causal relationship, and alternative etiologies are confirmed.

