- **Source Documents:** Medical records, laboratory reports, imaging films, and informed consent forms are stored in the hospital's medical record department or study office for 30 years after study completion.
- **Electronic Data:** The EDC database and backup files are stored on a secure server with restricted access. The data are retained for 30 years after study completion.
- **Statistical Analysis Data:** The locked database and statistical analysis code are stored in a secure location and retained for 30 years after study completion.

11. Statistical Analysis

(1) Statistical Analysis Sets

- **Full Analysis Set (FAS):** Includes all randomized subjects who receive at least one dose of the study drug. Missing efficacy data are imputed using the last observation carried forward (LOCF) method.
- **Per Protocol Set (PPS):** Includes subjects in the FAS who comply with the study protocol (e.g., complete all visits, receive all 4 doses of study drug, no major protocol violations). This set is used for sensitivity analysis of efficacy outcomes.
- **Safety Analysis Set (SAS):** Includes all subjects who receive at least one dose of the study drug. This set is used for safety analyses (adverse events, laboratory abnormalities).

(2) Descriptive Statistics

- **Continuous Variables:** Presented as mean \pm standard deviation (SD) for normally distributed data, or

median (P25, P75) for non-normally distributed data. Examples include age, NIHSS score, and infarct volume.

- **Categorical Variables:** Presented as frequency (percentage). Examples include gender, hypertension status, and mRS score categories (0-2 vs. 3-6).

(3) Inferential Statistics

- **Primary Efficacy Endpoint:** The proportion of subjects with mRS score 0-2 at Day 90 is compared between dose groups using the chi-square test or Fisher's exact test. A generalized linear model is used to adjust for potential confounders (e.g., age, baseline NIHSS score).
- **Secondary Efficacy Endpoints:**
 - Mean changes in NIHSS, MBI, and EQ-5D-5L scores from baseline are compared using repeated measures analysis of variance (ANOVA) or Kruskal-Wallis rank sum test.
 - The proportion of subjects with NIHSS score reduction ≥ 4 points at Day 14 is compared using the chi-square test.
- **Safety Endpoints:**
 - The incidence of AEs and SAEs is compared between dose groups using the chi-square test or Fisher's exact test.

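### A drug-related Grade 3 or higher AE removes the subject from the study, not only from the drug, so 90-day mortality and mRS can be missing because of toxicity

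*Protocol*

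**What the plan says.** Section 3(4), item 1 (Dose Adjustment), has two separate steps. Dosing is suspended for any Grade 3 or higher AE, and then "if the AE is judged to be related to the study drug, the subject withdraws from the study". Section 8(3), on Grade 3-4 AEs, also begins with immediate suspension of the drug and continues: "If the AE is related or probably related, the subject withdraws from the study, and follow-up continues until the AE resolves or stabilizes".

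Section 2(6) sets what is owed after withdrawal: "For withdrawn subjects, the investigator shall conduct a final safety assessment (if possible) and document the reason for withdrawal in the CRF". For AE or SAE withdrawals it adds treatment and follow-up of that event until it has resolved or is stable.

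Two rules in section 2(4) work in the same direction:

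- One ground for classing a subject as lost to follow-up is: "They experience an AE, SAE, or other complication that requires study termination and urgent treatment, as judged by the investigator".
- Of subjects whose stroke worsens after the study drug, it says "they shall withdraw from the study and be classified as an invalid case".

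The outcomes at risk are in section 5. Section 5(2) lists drug-related SAEs, all-cause mortality ("Proportion of subjects who die from any cause within 90 days of the first dose") and Grade 3 or higher laboratory abnormalities, all over 90 days. Section 5(3) lists mRS 0-2 at Day 90. For gaps in the data, section 11(1) says: "Missing efficacy data are imputed using the last observation carried forward (LOCF) method". Section 2(5) removes from the efficacy set any subject with "no post-baseline NIHSS or mRS assessment".

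**The concern.** Stopping a drug and leaving a study are different events. Stopping the drug protects the subject. Leaving the study ends data collection. Here the second follows automatically from drug-related toxicity, so whether a 90-day outcome is observed depends on whether the subject was harmed. That is the least favourable kind of missing data for a trial whose stated objective is safety and preliminary effectiveness.

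The rule also adds little protection. By section 3(2), item 4, dosing runs from Day 0 to Day 3. Before the last dose, suspension alone gives the same protection. After it, no exposure is left to avoid.

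**Working it through.** The protocol states no figure on this point, so there is none to reproduce. The check has two parts: what the text requires, and how often the rule would operate.

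**Reading the text**

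1. Suspension of the drug and withdrawal from the study are named as separate steps in both sections 3(4) and 8(3). The second cannot be read as loose wording for the first.
2. After withdrawal, section 2(6) requires one final safety assessment where feasible and follow-up of the triggering AE. No section requires the remaining scheduled visits, or vital status or mRS at Day 90.
3. A drug-related Grade 3-4 AE within 14 days of the first dose is DLT criterion 1 in section 5(1). The worsening-stroke rule in section 2(4) overlaps DLT criterion 2, an NIHSS rise of 4 or more.
4. The DLT is counted before the subject leaves, and section 2(5) keeps every dosed subject with safety data in the safety set. The escalation decision is therefore intact.
5. A death from the triggering AE would be seen through follow-up of that AE. A death after the AE has stabilised need not be. Routine AE monitoring ends 30 days after the last dose (sections 4(2) and 8(2)), which is Day 3 + 30 = Day 33. After that the Day 90 visit is the only scheduled contact.
6. For Day 90 mRS, LOCF carries forward a Day 14, Day 7 or baseline value, or section 2(5) drops the subject if nothing post-baseline exists. LOCF applies to efficacy data and supplies nothing for mortality.

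**Effect of one missing subject**

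With m of n outcomes missing, the observed proportion is undetermined over a width of m/n.

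- 1 of 6: 1/6 = 17 points. This is the usual case for an AE inside the DLT window, because one DLT in three brings the level to six.
- 1 of 3: 1/3 = 33 points. This applies to a related AE arising after the 14-day window, which does not trigger expansion.
- 2 of 6: 2/6 = 33 points.

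**How often the rule would operate**

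Let p be the per-subject probability of a drug-related Grade 3-4 AE. The protocol gives no value, so 5%, 10% and 20% are assumptions. Subjects are taken as independent, p as the same at every level, and every DLT as being of this type.

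- At least one such subject in the trial. With no event exactly 3 × 3 = 9 subjects are treated, so P = 1 − (1 − p)^9.
- A given level clears with exactly 1 DLT in 6 under section 1(2). There is one event in the first three and none in the next three: b = 3p(1 − p)^2 × (1 − p)^3 = 3p(1 − p)^5.
- At least one of three levels clears that way. With a = (1 − p)^3 (clears with 0 in 3) and s = 1 − a − b (does not clear), P = 1 − [s + a(s + a(s + a))].

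| p | a | b | s | ≥1 such subject in trial | a given level clears 1 in 6 | ≥1 of 3 levels clears 1 in 6 |
|---|---|---|---|---|---|---|
| 5% | 0.857 | 0.116 | 0.027 | 37% | 12% | 30% |
| 10% | 0.729 | 0.177 | 0.094 | 61% | 18% | 40% |
| 20% | 0.512 | 0.197 | 0.291 | 87% | 20% | 35% |

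The last two columns describe a dose that is passed as acceptable while its only toxicity case may have no Day 90 data.

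**The case against.** Several provisions narrow the gap. Section 10(3) locks the database only once all subjects have completed Day 90. Section 2(4) asks for every effort to complete the final safety assessment in subjects classed as lost. Section 8(6) follows AEs by visit, telephone or video until they settle. AE monitoring to 30 days after the last dose has no stated exception for withdrawn subjects. None of these reaches Day 90 for a withdrawn subject: the lock condition presumes the visit but does not order it, and the others end when the AE settles or at about Day 33. The core reading therefore stands.

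Three limits should be granted.

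- Late drug-related SAEs may be missed in every subject, because routine monitoring stops at about Day 33. The withdrawal rule is only part of that loss.
- The rates are assumed, and a triggering AE does not guarantee a missing outcome, since some subjects may still be seen. Section 5(1) has two other DLT criteria that the calculation sets aside.
- Escalation is unaffected, and efficacy by dose group will be weak at 6 to 18 subjects even with full follow-up. This limits the severity but is no reason to lose avoidable data.

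One could also read the withdrawal sentence as confined to the dosing days, since suspending a drug has meaning only then. The wording carries no such limit, and a withdrawal on Days 0 to 3 would lose still more follow-up.

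**Conclusion.** The concern holds. The protocol orders study withdrawal for drug-related severe toxicity and does not require the later scheduled outcomes, so 90-day vital status, 90-day laboratory safety and Day 90 mRS can be missing because of toxicity. Day 14 measures are also at risk if the AE comes first. DLT counting, the safety set and escalation are unaffected. One such subject is 17% of a six-subject level or 33% of a three-subject level. The probabilities above rest on assumed rates and show how often the rule would operate; they give neither the size nor the direction of the bias. This should be fixed before enrolment, though it does not undermine the dose-escalation design.

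**What to change.** Leave the drug-stopping and escalation rules as they are.

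- In sections 3(4) item 1 and 8(3), replace study withdrawal with permanent discontinuation of the study drug, the subject remaining in the study.
- Make the same change to the AE and SAE grounds of investigator-determined withdrawal in section 2(6), to the AE/SAE ground for loss to follow-up in section 2(4), and to the worsening-stroke rule there. The medication ground in section 2(6) could be aligned for consistency, but it is not a toxicity issue and can be decided separately.
- State that every subject who received at least one dose completes the Day 7, 14 and 90 assessments unless consent to follow-up is withdrawn. The minimum is NIHSS, mRS and vital status.

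The cost is protocol wording plus visits that are already scheduled. The full Day 14 and Day 90 visits include CTA/CTP, which may be unsuitable after a severe reaction. The minimum set avoids that and, for vital status, needs no more than a call. Sample size, dosing and escalation do not change.
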